For Week 12 CR100 rate, the Bayesian posterior distribution of the difference in the CR100 rate at Week 12 between the E6011 group and the placebo group is to be calculated. If there was a 50% or more probability of the difference between both groups being 25% or more, the efficacy of E6011 is confirmed. Noninformative prior distribution is to be used for both the E6011 group and the placebo group.

Subjects with missing primary endpoint data by Week 12 after administration due to premature discontinuation or other reasons are treated as treatment failures (non-responder imputation [NRI]).

Analysis of secondary endpoints

- CDAL response rate (CR70, CR100 (excluding Week 12)) and remission rate are to be calculated by treatment group and evaluation time. Summary statistics for CDAL value, change and percent change from baseline are also to be calculated by treatment group and evaluation time.
- PRO2 response rate (PRO2-CR5, PRO2-CR8) and remission rate are to be calculated by treatment group and evaluation time. Summary statistics for PRO2 value, change and percent change from baseline are also to be calculated by treatment group and evaluation time.
- SES-CD endoscopic response rate and endoscopic remission rate are to be tabulated by treatment group and evaluation time. Summary statistics for SES-CD value, change and percent change from baseline are also to be calculated by treatment group and evaluation time.
- Steroid-free remission rate and steroid-free response rate in subjects concomitantly using adrenocorticosteroids is to be tabulated by treatment group and evaluation time. Summary statistics for steroid dosage, change and percent change from baseline are also to be calculated for each treatment group and evaluation time.

Pharmacokinetics

Drug concentration is to be analyzed using the drug concentration analysis set. Summary statistics for serum E6011 concentration are to be calculated for each specified time. Serum E6011 concentration-time profile is also to be created.

Biomarkers, pharmacogenomics/pharmacogenetics

Biomarkers, pharmacogenomics/pharmacogenetics are to be analyzed using the pharmacodynamic analysis set. Summary statistics for serum total FKN concentration, faecal calprotectin and serum CRP concentration measured values, change and percent change from baseline are to be calculated by treatment group and evaluation time. CCI

[REDACTED] Details and results of the analysis of blood CD16⁺ monocytes, etc., blood CD16⁺ monocyte, etc. genetic markers and blood biomarkers (comprehensive proteome analysis) using the residual serum collected for this study are to be recorded in a separately created report, and not included in the Clinical Study Report.

Immunogenicity

Immunogenicity is to be analyzed using the safety analysis set. Incidence and ratio of serum anti-E6011 antibodies are to be calculated by treatment group and evaluation time. If anti-E6011 antibodies are confirmed, frequency and ratio of their neutralizing activity (if present) and isotypes are to be calculated.

Safety

Safety is to be analyzed using the safety analysis set. Summary statistics related to safety data (sample size, mean value, standard deviation, median value, minimum and maximum as continuous variables; sample size and ratio as categorical variables) are to be calculated by each treatment group based on the treatment that was administered. Safety endpoints include adverse events, clinical examination values, vital signs, weight, physical examination, standard 12-lead ECG tests, neurological symptoms and blood CD4⁺ cell count.

- Incidence rate of adverse events that occurred after the IMP administration is to be calculated by treatment group.
- Summary statistics for measured clinical examination values, vital signs and CD4⁺ cell count, as well as their change from baseline, are to be calculated by treatment group.
- For standard 12-lead ECG test findings and neurological symptoms, the numbers and rates are shown in the shift table by each treatment group and by normal and abnormal findings.

Interim analysis

No interim analysis is planned in this clinical trial.

Sample size Justification

The number of subjects in this clinical trial was determined considering operating characteristics pertaining to a simulation efficacy evaluation, with reference to efficacy performance in the E6011-J081-101 study, as well as efficacy performance of similar drugs. With 20 subjects allotted to each group, if the actual difference in CR100 response rate between the E6011 group and placebo group is 40% or more, the probability of confirming the efficacy of E6011 is above 80%.

Study schedule and anticipated date of completion

Recruitment: September 2018 to Mar 2022

Treatment: October 2018 to April 2022

Follow-up: Jun 2021 to April 2024

Close-out: May 2024

2. LIST OF ABBREVIATIONS

Abbreviations	Unabbreviated Terms (English)
BMI	Body mass index
CI	Confidence Interval
CDAI	Crohn's disease activity index
CRP	C-reactive protein
CV	Coefficient of variation
eCRF	electronic Case Report Form
FAS	full analysis set
FKN	Fractalkine
ICH	International Council for Harmonisation of Technical Requirements for Pharmaceuticals for Human Use
IMP	Investigation Medical Product (or Placebo)
JCV	JC virus
LLOQ	Lower Limit of Quantification
LOCF	Last Observation Carried Forward
MCMC	Markov chain Monte Carlo
MedDRA	medical dictionary for regulatory activities
MI	Multiple Imputation
OC	Observed Case
PD	Pharmacodynamics
PK	Pharmacokinetics
PML	progressive multifocal leukoencephalopathy
PPS	Per Protocol Set
PT	preferred term
SAP	Statistical Analysis Plan
SES-CD	simple endoscopic score for Crohn's disease
SD	Standard deviation
SOC	system organ class
TEAE	treatment emergent adverse events
WHO DD	world health organization drug dictionary

3. INTRODUCTION

This analysis plan gives a detailed description of the statistical methodologies, data listings, summary tables, and figures planned in the analyses of the data in the Early phase 2 clinical trial of E6011 in patients with active Crohn's disease study. The statistical data analyses, described in this document, is intended to provide unbiased and valid conclusions concerning the objectives of the study.

3.1 Study Population

Patients with Crohn's disease ranging from moderate to severe aged 18 or over and under 65 on the date of consent, diagnosed with small intestine-type, small and large intestine-type, or large intestine-type Crohn's disease at least 12 weeks before giving consent and that meet the rest of the inclusion/exclusion criteria

Approximately 40 subjects will be included in this clinical trial.

- E6011 group 20 subjects: Placebo group 20 subjects
- 22 Japanese subjects: 18 non-Japanese subjects (rough estimate)
- 8 biologic-naïve patients (rough estimate)

Subjects that meet all the following inclusion criteria and do not fall under any of the exclusion criteria shall receive the IMP.

3.2 Planned Study Design

This is a multinational, multicenter, randomized, double-blind, placebo-controlled, parallel-group, early phase 2 clinical trial. This clinical trial consists of a screening period, remission-induction period (double blind), rescue period (open-label), extension period (open-label), post-observation period and follow-up period. Administration of the IMP is to start after confirming eligibility at baseline (at week 0 before the start of the IMP administration) upon having carried out the screening test within 42 days prior to the start of the IMP administration after obtaining consent.

Patients with moderate to severe active Crohn's disease are to be randomly allocated to an E6011 10mg/kg group and a placebo group (1:1) using stratified allocation in which race (Japanese/non-Japanese) and history of previous use of biologics (yes/no) are used as allocation factors. The administration volume (about 100 mL) is to be prepared based on the weight of the subject by diluting E6011 with a physiological saline solution and infused intravenously over approximately 30 minutes. The physiological saline solution used to dilute E6011 is to be used as a placebo. The remission-induction period is to last 12 weeks, with E6011 or placebo administered in a double-blind method on Week 0, Week 1, Week 2, and once every two subsequent weeks up to Week 10, and the efficacy of E6011 is to be evaluated in Week 12. Subjects with a reduction in the CDAI of 70 or more (responders) compared to baseline at evaluation on Week 12 are to move on to the open-label extension period. The extension

period is to last 40 weeks, with 10 mg/kg of E6011 administered every four weeks from Week 12 to Week 48 and E6011 efficacy is to be evaluated at Week 52.

[figure not shown]
Subjects with less than 70 reduction on the CDAI (non-responders) at evaluation in Week 12 are to move on to the rescue period. The rescue period is to last 12 weeks, with additional administrations of 10 mg/kg of E6011 in Week 12, Week 13, Week 14 and every two subsequent weeks up to Week 22. Subjects with a reduction in the CDAI of 70 or more compared to baseline/Week 12 at evaluation in Week 24 of the rescue period are to move on to the open-label extension period. The extension period is to last 40 weeks, with 10 mg/kg of E6011 administered every four weeks from Week 24 to Week 60 and E6011 efficacy is to be evaluated at Week 64. Patients with less than 70 reduction in the CDAI compared to baseline and Week 12 at evaluation in Week 24 are to be discontinued.

The Principal Investigator or Sub-investigator is to confirm that the subjects' data as of Week 12 of the remission-induction period (double-blind) has been completely entered into the eCRF by the time the first evaluation in the rescue period or extension period takes place. Blinding in the double-blind period is to be maintained until a database in the double-blind study period is locked.

The post-observation period consists of an assessment in person 28 days after the completion or discontinuation of the extension period of the clinical trial, and an assessment in person or over the phone 70 days after the last administration of the IMP. The follow-up period entails contacting the patients over the phone, etc. every 6 months until 2 years have passed from the last administration of the IMP to inquire whether they have experienced progressive multifocal leukoencephalopathy (PML).

Figure 1 shows the design of the clinical trial.

Figure 1 Clinical trial design

Responders at CDAI evaluation on Week 12 of the remission-induction period are to move on to the extension period, in which E6011 is administered every four weeks. Non-responders are to move on to the rescue period, and if the CDAI has improved by Week 24, they are to move on to the extension period, in which E6011 administered every four weeks. Subjects whose CDAI has not improved by Week 24 are to be discontinued.

Table 1 to 3 shows the schedule for this clinical trial.

Table 1 Study Schedule (All Subjects)

Visit	Screening period	Remission-induction period (double-blind)										-
		1	2	3	4	5	6	7	8	9		
Test/Observation Time	Days -42 to -1 days	Week 0 ⁱ	Week 1	Week 2	Week 4	Week 6	Week 8	Week 10	Week 12	Discontinuation ^j		
Allowed deviations		—	± 1 day	± 3 days	—							
Signing of informed consent ^a		○										
Demographic characteristics, history of present illness		○										
Past medical history, complications		○										
Inclusion/exclusion criteria check		○	○									
Colonoscopy ^b		○								○	○	
IMP administration ^c			○	○	○	○	○	○	○	○ ^k		
Prior treatment and concomitant drugs/therapies		← →										
Physical findings		○	○	○	○	○	○	○	○	○	○	
Height/weight ^d		○	○		○	○		○		○	○	
Vital signs		○	○	○	○	○		○		○	○	
Standard 12-lead ECG		○								○	○	
Chest X-ray test		○										
Neurological symptoms ^e		○								○	○	
Anti-JCV antibody test		○									○	
Blood CD4 ⁺ cell test		○								○	○	
Viral test, tuberculosis test		○										
Pregnancy test ^f		○	○							○	○	
C. difficile toxin test		○										
CDAI, PRO2		○ ^g		○	○		○		○	○	○	
Haematology test, blood biochemistry test, urinalysis		○	○	○	○	○	○	○	○	○	○	
Adverse event		← →										
Serum E6011 concentration ^g ^h			○	○	○	○	○	○	○	○	○	
Serum anti-E6011 antibodies ^h			○		○	○		○		○	○	
Serum total FKN concentration ^h			○	○	○	○	○	○	○	○	○	
Blood CD16 ⁺ monocytes, etc. (FCM) ^h			○	○	○	○				○	○	
Blood CD16 ⁺ monocyte, etc. genetic markers ^h			○	○	○	○				○	○	
Faecal calprotectin			○		○	○		○		○	○	

a. A written consent of the subject is required prior to undergoing tests and medication washout as part of the requirements to participate in

this clinical trial.

- b. Endoscopic evaluations are performed by a centralized review.
- c. The IMP is to be administered after completing all assessments scheduled for that day (excluding serum E6011 concentration immediately after the end of administration).
- d. Height is measured during the screening period (on Visit 1) only.
- e. If abnormal neurological symptoms are found after IMP administration, the patient must be examined by a neurologist and undergo brain MRI (T1-weighted, FLAIR and diffusion-weighted imaging) within two weeks.
- f. Pregnancy test is conducted only in female subjects of childbearing potential.
- g. Blood samples are collected before and immediately after (within 10 minutes of) IMP administration between Week 0 and Week 10.
- h. Test results are to be retained by the testing laboratories and not to be shared with Principal Investigators, Sub-investigators and trial coordinators until code break. Blood CD16⁺ monocytes, etc. (FCM) is only conducted in Japanese subjects
- i. Randomization is to be performed at baseline (before the start of IMP administration in Week 0).
- j. As many specified tests and evaluations as possible should be conducted for the assessment at discontinuation.
- k. E6011 to be administered after the transition to the rescue period or Extension period.
- l. PML onset is to be investigated over the phone, etc. at six months, one year, one and a half years, and two years after the final IMP dose.
- m. E6011 not to be administered when discontinuing at Week 24 for a lack of CDAI response.
- n. To be conducted during the Week 24 visit or 28 days after discontinuation only when discontinuing at Week 24 for a lack of CDAI response.
- o. The hematocrit value used to calculate the CDAI score at Week 0 or screening test (screening test value may also be used if this is within 7 days of the date of the CDAI assessment).

Table 2 Study Schedule (Responders)

Visit	Extension period (open-label)												Post-observation period	Follow-up period
	10	11	12	13	14	15	16	17	18	19	-	20	21	
Test/Observation Time	Week 16	Week 20	Week 24	Week 28	Week 32	Week 36	Week 40	Week 44	Week 48	Week 52	Discontinuation	28 days after completion/discontinuation	70 days after last dose administration	2 years after last dose administration ¹
Allowed deviations	± 7 days	± 7 days	± 7 days	± 7 days	± 7 days	± 7 days	± 7 days	± 7 days	± 7 days	± 7 days	-	± 7 days	+7 days	± 1 month
Signing of informed consent ^a														
Demographic characteristics, history of present illness														
Past medical history, complications														
Inclusion/exclusion criteria check														
Colonoscopy ^b												○	○	
IMP administration ^c	○	○	○	○	○	○	○	○	○					
Prior treatment and concomitant drugs/therapies	← →													
Physical findings	○	○	○	○	○	○	○	○	○	○	○	○		
Height/weight ^d	○	○	○	○	○	○	○	○	○	○	○	○		
Vital signs	○	○	○	○	○	○	○	○	○	○	○	○		
Standard 12-lead ECG			○		○							○	○	
Chest X-ray test														
Neurological symptoms ^e		○			○							○	○	
Anti-JCV antibody test												○	○	
Blood CD4 ⁺ cell test						○						○	○	
Viral test, tuberculosis test														
Pregnancy test ^f												○	○	
C. difficile toxin test														
CDAI, PRO2	○	○	○	○	○	○	○	○	○	○	○	○		
Haematology test, blood biochemistry test, urinalysis	○	○	○	○	○	○	○	○	○	○	○	○	○	
Adverse event	← →													(PML)
Serum E6011 concentration ^g ^h	○	○	○	○	○	○	○	○	○	○	○	○		
Serum anti-E6011 antibodies ^h	○	○	○	○	○	○	○	○	○	○	○	○		
Serum total FKN concentration ^h														
Blood CD16 ⁺ monocytes, etc. (FCM) ^h			○								○	○		
Blood CD16 ⁺ monocyte, etc.			○								○	○		

genetic markers ^h												
Faecal calprotectin	○	○	○	○	○	○	○	○	○	○	○	

Table 3 Study Schedule (Non-responders)

Visit	Rescue period (open-label)							-
	10	11	12	13	14	15	16	
Test/Observation Time	Week 13	Week 14	Week 16	Week 18	Week 20	Week 22	Week 24	Discontinuation ^j
Allowed deviations	± 1 day	± 3 days	—					
Signing of informed consent ^a								
Demographic characteristics, history of present illness								
Past medical history, complications								
Inclusion/exclusion criteria check								
Colonoscopy ^b								
IMP administration ^c	○	○	○	○	○	○	(○) ^m	
Prior treatment and concomitant drugs/therapies	← →							
Physical findings	○	○	○	○	○	○	○	
Height/weight ^d		○	○		○		○	○
Vital signs	○	○	○		○		○	○
Standard 12-lead ECG							○	○
Chest X-ray test								
Neurological symptoms ^e							○	○
Anti-JCV antibody test							(○) ⁿ	○
Blood CD4 ⁺ cell test							○	○
Viral test, tuberculosis test								
Pregnancy test ^f							○	○
C. difficile toxin test								
CDAI, PRO2		○	○		○		○	○
Haematology test, blood biochemistry test, urinalysis	○	○	○	○	○	○	○	○
Adverse event	← →							
Serum E6011 concentration ^g ^h	○	○	○	○	○	○	○	○
Serum anti-E6011 antibodies ^h		○	○		○		○	○
Serum total FKN concentration ^h								
Blood CD16 ⁺ monocytes, etc. (FCM) ^h								
Blood CD16 ⁺ monocyte, etc. genetic markers ^h								
Faecal calprotectin		○	○		○		○	○

Visit	Extension period (open-label)												Post-observation period		Follow-up period
	17	18	19	20	21	22	23	24	25	26	-	27	28		
Test/Observation Time	Week 28	Week 32	Week 36	Week 40	Week 44	Week 48	Week 52	Week 56	Week 60	Week 64	Discontinuation	28 days after completion/disccontinuation	70 days after last dose administration	2 years after last dose ¹ administration	
Allowed deviations	± 7 days	± 7 days	± 7 days	± 7 days	± 7 days	± 7 days	± 7 days	± 7 days	± 7 days	± 7 days	-	± 7 days	+7 days	± 1 month	
Signing of informed consent ^a															
Demographic characteristics, history of present illness															
Past medical history, complications															
Inclusion/exclusion criteria check															
Colonoscopy ^b												○	○		
IMP administration ^c	○	○	○	○	○	○	○	○	○	○					
Prior treatment and concomitant drugs/therapies															
Physical findings	○	○	○	○	○	○	○	○	○	○	○	○			
Height/weight ^d	○	○	○	○	○	○	○	○	○	○	○	○			
Vital signs	○	○	○	○	○	○	○	○	○	○	○	○			
Standard 12-lead ECG			○			○			○		○	○			
Chest X-ray test															
Neurological symptoms ^e	○				○				○		○	○			
Anti-JCV antibody test											○	○	(○) ⁿ		
Blood CD4 ⁺ cell test					○				○		○	○			
Viral test, tuberculosis test															
Pregnancy test ^f									○		○	○			
C. difficile toxin test															
CDAI, PRO2	○	○	○	○	○	○	○	○	○	○	○	○			
Haematology test, blood biochemistry test, urinalysis	○	○	○	○	○	○	○	○	○	○	○	○			
Adverse event	↔												(PML)		
Serum E6011 concentration ^g ^h	○	○	○	○	○	○	○	○	○	○	○	○			
Serum anti-E6011 antibodies ^h	○	○	○	○	○	○	○	○	○	○	○	○			
Serum total FKN concentration ^h															
Blood CD16 ⁺ monocytes, etc. (FCM) ^h															
Blood CD16 ⁺ monocyte, etc. genetic markers ^h															
Faecal calprotectin	○	○	○	○	○	○	○	○	○	○	○	○			

3.3 Study Objectives

3.3.1 Primary Objectives

- To examine the efficacy and safety of E6011 at 12 weeks after administration by means of double-blind placebo-controlled trial.

3.3.2 Secondary objectives

- To examine the efficacy and safety of a long-term administration of E6011.
- To evaluate the pharmacokinetics and immunogenicity of E6011.

3.3.3 Exploratory objectives

CCI

4 ANALYSIS ENDPOINTS

4.1 Baseline Definition

As a rule, baseline values are defined as the last available value prior to the first injection of E6011 for all longitudinal endpoints unless explicitly stated otherwise in this document. As defined per protocol all assessments are performed before the IMP administration.

Change from baseline values are defined as:

Value measured after first dosing – Baseline value

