#### 9.5.1.5.1 Adverse event

An adverse event (AE) is any untoward medical occurrence in a subject. An AE does not necessarily have a causal relationship with an IMP. In the present trial, IMP refers to E6011 and the placebo.

In this clinical trial, an AE is defined as follows.

- Any undesirable or unintended sign (including an abnormal laboratory value), symptom, or illness
  that emerges after signing informed consent, whether or not it has a causal relationship with the
  IMP. When an illness is diagnosed based on signs and symptoms, the illness, rather than
  individual signs/symptoms, is treated as an AE.
- An illness that emerges or aggravation of a pre-existing illness.
- A laboratory value or worsening of a test (e.g., ECG, X-rays) indicative of some symptom (including tests not prescribed by the protocol).
- A laboratory value or worsening of a test (e.g., ECG, X-rays) that results in a change of treatment method or discontinuation of the clinical trial (including tests not specified in the protocol).
- Recurrence of an episodic medical condition (e.g., headaches) that was not present at the time of signing informed consent.
- An abnormal laboratory value that requires some form of intervention, or discontinuation or interruption of treatment with the IMP, whether or not it is identified in the protocol.

Note that worsening of the underlying disease (Crohn's disease) is not treated as an AE (minor fluctuations in CDAI and SES-CD scores are accounted for in efficacy evaluations but are not regarded as

AEs), except when it worsens beyond expectations (e.g., requiring hospitalization or surgery).

All AEs that emerge after signing of informed consent and up to 70 days after the final dose of the IMP are to be compiled and recorded in case report forms, whether or not they have a causal relationship with the IMP or study procedures. For screening failure subjects whose reason for failure is the onset of an AE, the name and seriousness of the AE are to be documented in their case report forms.

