4.5 Efficacy endpoints

4.5.1 Primary Endpoints for Efficacy

- CR100 response rate at Week 12, defined as ratio of patients who had CDAI reductions of at least 100 points from baseline to Week 12. CDAI score will be considered as collected in the eCRF by the investigator.

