5 ANALYSIS POPULATIONS

5.1 Efficacy Populations

FAS (full analysis set) is a set of subjects to whom the IMP has been administered after randomization, and who had 1 or more evaluable, post-IMP administration primary efficacy endpoint (i.e., to have an evaluable CDAI value at baseline and any other post baseline).

PPS (per protocol set) is a set of subjects who has been randomized and satisfactorily ended the remission induction treatment period, subjects that fulfill all inclusion /exclusion criteria and have no major or critical protocol violations.

Patients in the efficacy populations will be analyzed according to the treatment group allocated by the randomization even if not treated with the correct treatment assigned.

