- 2) Rescue Period (Open label): comprises from week 12 to week 24 for non-responders. Subjects with a reduction in the CDAI of less than 70 compared to baseline after finishing evaluation in Week 12 of the remission-induction period are to move on to the rescue period. The rescue period is to last 12 weeks, with 10 mg/kg of E6011 administered in an unblinded manner on Week 12, Week 13, Week 14 and every two subsequent weeks until Week 22.
- 3) Extension Period (Open label): comprises from week 12 to week 52 for responders at week 12 and from week 24 to week 64 for non-responders at week 12. Subjects who

finished evaluation at Week 12 of the remission-induction period and had a CDAI response of 70 or more, and subjects who moved on to the rescue period and finished evaluation at Week 24 with a CDAI response of 70 or more are to move on to their respective extension period. The extension period is to last 40 weeks, with 10 mg/kg E6011 administered in an unblinded manner every four weeks up to Week 48(responders) or Week 60(non-responders).

- 4) Post-Observation Period: After the extension period of the clinical trial has been finished or discontinued, examinations are to be carried out 28 days after the completion or discontinuation of the extension period and 70 days after the last administration of the IMP.
- 5) Follow-up Period: PML onset is to be investigated over the phone, etc. every 6 months in the two-year follow-up period after the last IMP administration.

Four analysis periods are defined:

- 1) Remission-induction period: as defined above.
- 2) Rescue period: as defined above. This period will be used only for adverse events endpoints.
- 3) Entire administration period comprises the remission-induction period, the rescue period, the extension period and the post-observation period as defined above.
- 4) Follow-up period: as defined above.

Analyses of the remission-induction period will be performed after the remission-induction period is completed. Analyses of the entire administration period (remission-induction period, rescue period, extension period and post-observation period) will be performed after the post-observation period is completed. Analysis of the follow-up period will be performed after the follow-up period is completed.

In all TFLs that are displayed by treatment groups they will refer to the remission-induction treatments.

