6.8.1 Primary Efficacy analysis

Primary analysis aims to determine if the treatment effect in CR100 response rate at Week 12 is expected to be higher for patients treated with E6011 than for patients treated with placebo.

The Bayesian posterior distribution of the difference in the CR100 rate at Week 12 between E6011 (p1) and placebo (p2) is obtained as p1-p2 posterior distributions. Non-informative prior (Jeffreys) Beta (1/2, 1/2) distributions described by (Oleksandr Sverdlov, Yevgen Ryeznik, & Sheng Wu, January 1, 2015) will be used to calculate p1 and p2 posterior distributions.

A MCMC algorithm will be performed using the following parameters:

- Number of chains = 3
- Initial values for the algorithm in every chain= 3 starting values simulated by a Beta (0.5, 0.5)
- Number of Burn-in = 100000

- Number of Iterations = 200000

Diagnostic for the MCMC convergence will be checked through the Geweke Diagnostics test, Raftery-Lewis Diagnostics, Gelman-Rubin convergence and the autocorrelation efficiency. In case of any issue due to an autocorrelation or non-convergence of the algorithm, the size of the burn-in, the number of iterations and a possible thinning will be evaluated.

Efficacy of E6011 will be confirmed if there was a 50% or more probability of the difference between both groups being 25% according to the posterior distribution.

Probability of the difference between groups being greater than zero will be also calculated.

Subjects with missing primary endpoint data due to premature discontinuation before 12 weeks after administration, or other reasons are treated as non-responders (NRI) in the modeling of the endpoint.

Primary analysis will be performed in the FAS population, and in the PPS population as a supportive analysis.

Two sensitivity analysis will be performed a Last Observation Carried Forward (LOCF) and an Observed Case (OC) imputation for CDAI at week 12 will be used instead of NRI.

Another supportive analysis will be performed following the same logistic regression model (randomization strata and treatment group as fixed factor) used in the secondary analysis.

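### SAP 4.1 ties baseline to the first E6011 injection, which placebo subjects receive at Week 12 or never; the rule is wrong as written for the placebo arm, although Week 0 is clearly meant.

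*SAP*

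**What the plan says.** **The formal rule.** SAP 4.1 defines baseline as "defined as the last available value prior to the first injection of E6011 for all longitudinal endpoints unless explicitly stated otherwise in this document". The change formula in the same section subtracts that baseline from a value measured after first dosing, without saying which dosing. The sentence between the two speaks of IMP rather than E6011.

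**What depends on it.** The primary endpoint in SAP 4.5.1 is "defined as ratio of patients who had CDAI reductions of at least 100 points from baseline to Week 12" and gives no baseline definition of its own. The FAS in SAP 5.1 requires subjects "to have an evaluable CDAI value at baseline and any other post baseline". SAP 6.8.1 has subjects with missing Week 12 data "treated as non-responders (NRI) in the modeling of the endpoint".

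**What the arms receive.** Protocol 9.5.1.5.1 states: "In the present trial, IMP refers to E6011 and the placebo". The SAP abbreviation list also includes placebo under IMP. E6011 is therefore not a synonym for study drug. SAP 3.2 makes placebo the saline diluent and gives E6011 to every continuing subject from Week 12, in either the extension or the rescue period (schedule footnote k). Footnote c to the same schedule places dosing after that day's assessments.

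**The concern.** A baseline rule for a randomised comparison has to mean the same thing in both arms. This one means Week 0 for E6011 subjects. For continuing placebo subjects it means Week 12, and for placebo subjects who stop earlier it means nothing.

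The decision rule rests on CR100 at Week 12, which is a change from baseline, and every change-from-baseline table relies on the same definition. Read literally, the rule removes placebo response from the primary comparison. It could also drop from the FAS the early placebo dropouts whom non-responder imputation is meant to count.

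**Working it through.** **1. Applying 4.1 to each kind of subject**

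| Subject | First E6011 | Last CDAI before it | Week 12 change under literal 4.1 |
|---|---|---|---|
| E6011 arm | Week 0 | Week 0 | Week 12 minus Week 0, as intended |
| Placebo, continues after Week 12 | Week 12, after assessments | Week 12 | Week 12 minus Week 12 = 0 |
| Placebo, stops before Week 12 | Never | No anchor | No baseline, so undefined |

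If first dosing in the change formula also means first E6011, the Week 12 value of a continuing placebo subject is not even a post-dosing value. On either reading a fall of 100 points is impossible, so placebo CR100 at Week 12 is 0% by construction.

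**2. Comparing 4.1 with the other uses of baseline**

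- Explicitly Week 0 or Day 1: SAP synopsis inclusion criterion 3; SAP 3.2 (design text and schedule footnote i); the SAP 6.6 windows table (Baseline, target day 1); Protocol 9.1 and 9.3.1 criterion 3.
- Implicitly before Week 12: SAP 3.2 makes the rescue-exit decision on CDAI reduction "compared to baseline and Week 12 at evaluation in Week 24", which treats the two as separate references. SAP 6.1 defines rescue entry as "Subjects with a reduction in the CDAI of less than 70 compared to baseline after finishing evaluation in Week 12".
- Implicitly before Week 2: SAP 6.8.2 tabulates change from baseline at Weeks 2, 4, 8 and 12 in both groups, and accumulates steroid dose from baseline to Week 2.
- Own anchor: the SES-CD response endpoint in SAP 4.5.2 is measured from before IMP. No such statement is attached to the CDAI or PRO2 endpoints.

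**3. Reproducing the plan's own figure**

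Inputs from SAP 6.8.1, the SAP synopsis and SAP 8: Jeffreys priors Beta(0.5, 0.5) in each arm; success if P(p1 − p2 ≥ 0.25 | data) ≥ 0.50; 20 per arm; stated probability of success above 80% at a true difference of 40 points.

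The posteriors are p1 ~ Beta(0.5 + x1, 0.5 + n1 − x1) for E6011 and p2 ~ Beta(0.5 + x2, 0.5 + n2 − x2) for placebo. All 21 × 21 outcomes were enumerated. The documents give no placebo CR100 rate, so it was assumed to lie between 5% and 60%, with the E6011 rate 40 points higher. The probability of success is 80.7% to 87.4%, so the stated figure holds when Week 0 is the baseline in both arms.

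**4. Illustration of the literal rule**

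The threshold is the smallest x1 with posterior probability of at least 0.50. The placebo counts of 2, 4 and 6 are assumptions.

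| Placebo responders, 20 per arm | Posterior just below | Posterior at threshold | E6011 responders needed |
|---|---|---|---|
| 0/20 (forced by literal 4.1) | x1 = 5: 0.430 | x1 = 6: 0.618 | 6/20 |
| 2/20 (Week 0 baseline) | x1 = 7: 0.461 | x1 = 8: 0.614 | 8/20 |
| 4/20 (Week 0 baseline) | x1 = 9: 0.473 | x1 = 10: 0.610 | 10/20 |
| 6/20 (Week 0 baseline) | x1 = 11: 0.477 | x1 = 12: 0.607 | 12/20 |

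Protocol 9.7.2 records 25 enrolled. With an assumed split of 12 E6011 and 13 placebo, the threshold is 4/12 with placebo forced to 0/13 (posterior 0.657). With a Week 0 baseline it is 6/12 at 2/13 (0.672) or 3/13 (0.509), and 7/12 at 4/13 (0.524).

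The forced-zero rows keep every placebo subject in the analysis as a non-responder. If early placebo dropouts left the FAS for want of a baseline, the placebo denominator would be smaller than shown.

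**The case against.** The strongest reply is that nobody would program this. SAP 4.1 yields to explicit statements elsewhere in the SAP. Inclusion criterion 3 names Week 0 as baseline in the same item as the CDAI and PRO2 limits, and the windows table puts Baseline at Day 1 for both arms. The literal reading also makes the design unworkable: no placebo subject could show the 70-point fall that routes directly to the extension, the two references for rescue exit would coincide, and placebo tables at Weeks 2, 4 and 8 would precede their own baseline. SAP 6.11 declares no departure from the protocol, and SAP 6.1 calls the analysis exploratory.

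Most of this stands. It settles the intent and makes an unnoticed error unlikely. It does not make the rule correct. Criterion 3 governs eligibility, and the windows table assigns visits to days; neither says which value is subtracted in the CDAI endpoint. SAP 4.1 is the only formal rule.

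Two stronger readings should be resisted:

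- A reader might infer that the whole placebo arm would drop out of the FAS, so that the success threshold could rise as well as fall. SAP 5.1 does not support this. It asks for any post-baseline CDAI and does not confine it to the first 12 weeks. Continuing placebo subjects have scheduled CDAI from Week 14 (rescue) or Week 16 (extension). Only placebo subjects who stop before any E6011 lack a baseline.
- A reader might infer that the authors chose a Week 12 baseline for placebo, or that the thresholds above forecast a biased result. The documents point to loose wording, and the thresholds apply only if that wording is programmed as it stands.

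**Conclusion.** The point holds as an error of wording in the SAP's only formal baseline definition. It should be corrected before programming. It is not evidence of a flawed design or of a result already compromised.

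That the wording is wrong for placebo subjects, and inconsistent with Week 0 elsewhere, follows directly from the text. If it were followed literally, placebo CR100 at Week 12 would be 0% by construction. At 20 per arm the E6011 count needed would then fall to 6, from the 8 to 12 required under the assumed placebo counts. That size depends on literal programming, on all placebo subjects being kept as non-responders, and on placebo counts the documents do not give. With a Week 0 baseline the stated probability of success is unaffected.

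**What to change.** In SAP 4.1, replace the reference to the first E6011 injection with *first administration of double-blind IMP (E6011 or placebo) at Week 0*. SAP 4.4 already uses nearly this wording for exposure. Tie first dosing in the change formula to the same dose.

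A pre-E6011 reference may be wanted for open-label summaries of placebo subjects, since SAP 6.8 analyses efficacy over the entire administration period. If so, give it a separate name and confine it to tables after Week 12.

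The cost is two phrases, plus one sentence if the second reference is wanted. The core correction needs no added data or analysis and changes nothing in clinical conduct.
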